5.2. Baseline Disease Characteristics

The following study baseline disease characteristics will be summarized for Safety Analysis Set by treatment group and overall, using data collected prior to or on **Study Day 1**:

- HIV-1 RNA categories (copies/mL): (a) < 50, (b) ≥ 50
- CD4+ cell count (/μL)
- CD4+ cell count categories (/ μ L): (a) < 50, (b) \geq 50 to < 200, (c) \geq 200 to < 350, (d) \geq 350 to < 500, and (e) \geq 500
- CD4 percentage (%)
- HIV risk factors (mode of infection)
- HIV disease status
- eGFR_{CG} at Study Baseline (mL/min)
- Duration of prior ARV treatment (years)
- Log₁₀ HCV RNA at Study Baseline (log₁₀ IU/mL)
- HCV RNA Category at Study Baseline: (a) < 800,000 IU/mL; (b) $\ge 800,000 \text{ IU/mL}$

In summary of disease characteristics at the study baseline, for categorical data, the Cochran-Mantel-Haenszel (CMH) test (general association statistic for nominal data, and row means scores differ statistic for ordinal data) will be used to compare the 2 treatment groups. For continuous data, the 2-sided Wilcoxon rank sum test will be used to compare the 2 treatment groups.

The following Part 2 baseline disease characteristics will be summarized for Part 2 Safety Analysis Set by treatment group and total within each HCV genotype (1a, 1b, and other if applicable) and overall, using data collected prior to or on **Part 2 Day 1**:

- Log₁₀ HCV RNA at Part 2 Day 1 (log₁₀ IU/mL)
- HCV RNA Category at Part 2 Day 1: (a) < 800,000 IU/mL; (b) $\ge 800,000 \text{ IU/mL}$
- IL28B
- Cirrhosis
- Cirrhosis determination method
- ALT at Part 2 Baseline
- ALT category at Part 2 Baseline: (a) $\leq 1.5 \times \text{ULN}$; (b) $> 1.5 \times \text{ULN}$
- Prior HCV treatment experience: (a) treatment-naïve; (b) treatment-experienced
- eGFR_{CG} at Part 2 Baseline (mL/min)

In summary of disease characteristics at Part 2 baseline, no between treatment p-value will be calculated.

5.3. Medical History

General medical history data will be collected at screening and listed only. General medical history data will not be coded.

A by-subject listing of disease-specific medical history will be provided by subject ID number (in ascending order) and medical history of abnormalities (in chronological order).

FTC/RPV/TAF

6. EFFICACY ANALYSES

The efficacy analyses include analyses of both HCV study drug (LDV/SOF) efficacy and HIV study drug (E/C/F/TAF and F/R/TAF) efficacy. The analysis of HCV efficacy endpoints will use HCV FAS, and the analysis of HIV efficacy endpoints will use HIV FAS.

In efficacy analysis, HCV efficacy data (HCV RNA) collected from the first dose date of LDV/SOF up to the last dose date of LDV/SOF + 3 days are considered **on-HCV-treatment** data; HIV efficacy data (HIV-1 RNA, CD4+ cell count, and CD4%) collected from the first dose date of HIV study drug up to the last dose date of HIV study drug + 1 day are considered **on-HIV-treatment** data.

6.1. Primary Efficacy Endpoint

6.1.1. Definition of Primary Efficacy Endpoint

The primary efficacy endpoint is SVR12 defined as HCV RNA < LLOQ 12 weeks after discontinuation of LDV/SOF in the HCV FAS. The COBAS® AmpliPrep/COBAS® TaqMan® HCV Quantitative Test, v2.0 will be used to mearsure HCV RNA. The LLOQ for this assay is 15 IU/mL.

6.1.2. Statistical Hypothesis for the Primary Efficacy Endpoint

In the primary efficacy analysis, the SVR12 rate for each of the two treatment groups will be compared to the performance goal of 88% using a 2-sided exact 1-sample binomial test at the 0.025 significant level. The null (H_0) and alternative (H_1) hypotheses used to assess superiority of LDV/SOF relative to the performance goal of 88% are:

 H_0 : SVR12 = 88%

 H_1 : SVR12 \neq 88%

It is difficult to characterize a single historical control rate for the HIV/HCV coinfection population in this study. Given these difficulties, rather than use a historical control rate as the basis for assessing the primary endpoint, a performance goal was defined as a benchmark against which the efficacy of LDV/SOF will be tested. The benchmark sets a higher comparator bar of 88%. The basis for this benchmark includes the overall trend toward increasing SVR rates in recent years; and the general appeal of using a fixed clinically relevant threshold as a measure of treatment benefit {Weins 2013} of LDV/SOF for the HIV/HCV coinfection population.

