8.4. Efficacy Analysis

8.4.1. Primary Analysis

The primary efficacy endpoint is SVR12 (HCV RNA < LLOQ 12 weeks after discontinuation of therapy). The primary analysis will be performed after all enrolled subjects have been followed through post-HCV treatment Week 12 or discontinued from study.

In the primary efficacy analysis, the SVR12 rate will be compared to the performance goal of 88% by using two-sided exact one-sample binomial test at the 0.05 significance level. The basis for this benchmark includes the overall trend toward increasing SVR rates in recent years; and the general appeal of using a fixed clinically relevant threshold as a measure of treatment benefit of LDV/SOF.

The null (H_0) and alternative (H_1) hypotheses used to assess superiority of LDV/SOF relative to the performance goal of 88% are:

- $H_0: SVR12 = 88\%$
- $H_1: SVR12 \neq 88\%$

The primary efficacy analysis will also include the construction of an associated two-sided exact 95% CI.

Furthermore, SVR12 will also be summarized by the HIV treatment arms (F/TAF-based regimen).

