8.8. Sample Size

A sample size of 120 subjects will provide at least 85% power to detect an improvement of at least 8 percentage points in SVR12 rate from the performance goal of 88% by using a two-sided exact one-sample binomial test at significance level of 0.05.

9. **RESPONSIBILITIES**

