1.3. Sample Size and Power

A sample size of 120 subjects will provide at least 85% power to detect an improvement of at least 8% in overall SVR12 rate from the performance goal of 88%, by using a 2-sided exact 1-sample binomial test at a significance level of 0.05.

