3.5. Multiple Comparisons

The study has defined a single primary endpoint of SVR12, which will only be analyzed at the Post HCV Week 12 analysis. Therefore, there is no multiple comparison issue.

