6.1.3. Primary Analysis of the Primary Efficacy Endpoint

The 2-sided exact 1-sample binomial test will be used to test the statistical hypotheses described above. The 2-sided 95% exact confidence interval (CI) based on the Clopper-Pearson method {Clopper 1934} will be provided for the SVR12 rate for each of the two treatment groups in HCV FAS.

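### The SAP's primary SVR12 analysis tests each HIV arm at 0.025 instead of the protocol's single overall test at 0.05, so the claimed power of at least 85% becomes about 30% per arm

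*SAP*

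**What the plan says.** Protocol 8.4.1 defines a single primary comparison: "the SVR12 rate will be compared to the performance goal of 88% by using two-sided exact one-sample binomial test at the 0.05 significance level", with an exact 95% interval. It adds that SVR12 will be summarised by HIV arm and attaches no test to that summary. Protocol 8.8 sizes the trial for this comparison: "A sample size of 120 subjects will provide at least 85% power" for a gain of 8 percentage points over 88%.

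The SAP is not consistent with the protocol or with itself:

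- **SAP 1.3** repeats the protocol's power statement, explicitly for the pooled rate and at 0.05: "A sample size of 120 subjects will provide at least 85% power to detect an improvement of at least 8% in overall SVR12 rate".
- **SAP 6.1.2** moves the primary test to the individual arms: "the SVR12 rate for each of the two treatment groups will be compared to the performance goal of 88" per cent, "using a 2-sided exact 1-sample binomial test at the 0.025 significant level".
- **SAP 6.1.3** attaches the interval to each arm separately and keeps the conventional level: "The 2-sided 95% exact confidence interval (CI) based on the Clopper-Pearson method".
- **SAP 3.5** argues from the single primary endpoint and concludes: "Therefore, there is no multiple comparison issue".
- **SAP 6.2.2.1** applies the SVR12 methods unchanged to SVR4, so SVR4 inherits the same test.

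**The concern.** The test that was powered is not the test the SAP will run. Halving the sample and halving alpha both cost power, and the power figure in SAP 1.3 was not revised.

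Three further gaps follow:

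- With two primary tests, the SAP does not say whether the trial succeeds if one arm passes or only if both do.
- A 95% interval does not correspond to a two-sided 0.025 test, so the p-value and the interval can point in opposite directions for the same arm.
- I found no statement in the SAP that this departs from the protocol.

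If the SAP is followed, an arm performing exactly as the design assumes would usually not be declared better than 88%, and the pooled question the trial was built to answer would have no primary test. If the conflict is left open, the choice between two primary tests could be made after results are known.

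**Working it through.** **Inputs**

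- Null rate 0.88 (Protocol 8.4.1, SAP 6.1.2).
- Assumed true rate 0.88 + 0.08 = 0.96 (Protocol 8.8, SAP 1.3).
- n = 120 in total, about 60 per arm, randomised 1:1 (Protocol synopsis, SAP 1.2.2).
- Two-sided alpha: 0.05 for the overall test (Protocol 8.4.1, SAP 1.3); 0.025 per arm (SAP 6.1.2).
- Neither document gives a dropout allowance. The first calculation takes all randomised subjects into the HCV full analysis set.

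**Method**

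The critical value r is the smallest count with P(X ≥ r | n, 0.88) ≤ alpha/2. Power is P(X ≥ r | n, 0.96). X is binomial. The minimum-likelihood form of the two-sided exact test gives the same critical values in both designs below.

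**1. The plan's own figure (n = 120, alpha 0.05, upper tail 0.025)**

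- P(X ≥ 112 | 120, 0.88) = 0.0411, too large.
- P(X ≥ 113 | 120, 0.88) = 0.0192, so r = 113.
- Power = P(X ≥ 113 | 120, 0.96) = 0.891.

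The statement of at least 85% is correct for the overall test.

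**2. The test in SAP 6.1.2 (n = 60, alpha 0.025, upper tail 0.0125)**

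- P(X ≥ 58 | 60, 0.88) = 0.0196, too large.
- P(X ≥ 59 | 60, 0.88) = 0.0043, so r = 59, an observed rate of 98.3%.
- Power = P(X = 59) + P(X = 60) = 60 × 0.96^59 × 0.04 + 0.96^60 = 0.2159 + 0.0864 = 0.302.

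**3. At trial level, arms independent and both at 96%**

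- At least one arm passes: 1 − (1 − 0.302)² = 0.513.
- Both arms pass: 0.302² = 0.091.

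**4. Sensitivity**

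| Assumption | Power per arm |
|---|---|
| n = 60, true rate 95% | 19.2% |
| n = 60, true rate 97% | 45.9% |
| n = 60, true rate 98% | 66.2% |
| n = 60, true rate 99% | 87.9% |
| n = 51, true rate 96% | 39.0% |
| n = 55, true rate 96% | 34.9% |
| n = 64, true rate 96% | 26.9% |
| n = 65, true rate 96% | 51.5% |

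The jump between 64 and 65 comes from discreteness: at 65 the rule first tolerates two failures.

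**5. Interval against test**

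Take 58/60 in one arm (96.7%).

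- Exact two-sided p = 2 × 0.0196 = 0.039 (0.044 by minimum likelihood). It fails at 0.025.
- 95% Clopper-Pearson interval, as planned in SAP 6.1.3: 88.5% to 99.6%. It excludes 88%.
- 97.5% interval, which matches the test: 87.1% to 99.7%. It includes 88%.

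**6. The same data under the two documents**

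Suppose both arms have 58/60, so 116/120 overall. The protocol's test gives p = 2 × 0.0008 = 0.0016, with a 95% interval of 91.7% to 99.1%: clear success. Under SAP 6.1.2 both arms fail.

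**The case against.** Several points can fairly be made for the SAP.

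- **An overall estimate is still planned.** SAP 6.3.2.2 and 6.3.2.4 include exact 95% intervals for HCV RNA below LLOQ that can be read as pooled over arms. If so, a reader could check whether the pooled interval excludes 88%. That stands, but these are tertiary displays with no hypothesis test, and they do not replace the primary analysis.
- **30% against 85% compares one arm with a whole trial.** Under an either-arm rule, which alpha splitting would suit, the comparable figure is 51%. That is right, and it is why the trial-level range of 9% to 51% is given. Both ends are far below 85%.
- **0.025 may be a one-sided level mislabelled as two-sided.** That would agree with the 95% interval. The critical value is then 58/60 and power is 56.8% per arm: 1 − (1 − 0.568)² = 81% for either arm, with no adjustment for two tests, and 0.568² = 32% for both. Still below 85%.
- **Type I error is not inflated.** Two tests at 0.025 keep the familywise error at or below 0.05. I agree. SAP 3.5 is inconsistent with 6.1.2, but it does no harm to error control.
- **The departure may be declared elsewhere.** SAP 7.7 covers safety analyses only, and the revision table is empty. The copy reviewed lacks some text around 6.3.1, so a statement there cannot be excluded. Even if there is one, SAP 1.3 and 6.1.2 still conflict.

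**Conclusion.** The concern holds and should be fixed before the final analysis. SAP 6.1.2 and 6.1.3 specify a different primary test from Protocol 8.4.1, and the power in SAP 1.3 belongs to the protocol's test. At a true SVR12 rate of 96%, power falls from 89.1% for the overall test to 30.2% per arm, or between 9.1% (both arms) and 51.3% (either arm) at trial level.

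These figures assume 60 subjects per arm in the HCV full analysis set, and the trial-level ones also assume independent arms with equal rates. Between 51 and 65 subjects per arm, the per-arm figure stays within about 27% to 52%. It reaches 85% at n = 60 only if the true rate is close to 99%.

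**What to change.** **Preferred: return to the protocol.**

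- In SAP 6.1.2, test the overall SVR12 rate in the HCV full analysis set against 88% with the two-sided exact binomial test at 0.05.
- In SAP 6.1.3, give the overall 95% Clopper-Pearson interval as the primary estimate. Show each arm's rate with a 95% interval, labelled descriptive.
- SAP 6.2.2.1 can then stand, with SVR4 following the revised method. SAP 1.3 and 3.5 become correct as written.

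**If per-arm testing is intended:**

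- Restate power in SAP 1.3 as about 30% per arm.
- State whether success needs one arm or both.
- Use 97.5% intervals to match the 0.025 tests.
- Rewrite SAP 3.5 to explain the alpha split.
- Record the change from the protocol with its reason.

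Either way the cost is SAP wording, with no extra subjects or data. Because the trial is open-label and SAP 2.1 plans an administrative look at all efficacy data through post-treatment Week 4, the amendment should be dated and say whether it came before that look. Restoring the protocol's test is the easier change to defend, since that test was specified in advance.

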6.1.3. Primary Analysis of the Primary Efficacy Endpoint

The 2-sided exact 1-sample binomial test will be used to test the statistical hypotheses described above. The 2-sided 95% exact confidence interval (CI) based on the Clopper-Pearson method {Clopper 1934} will be provided for the SVR12 rate for each of the two treatment groups in HCV FAS.

6.1.4. Subgroup Analysis of the Primary Efficacy Endpoint

The point estimates and 95% exact CIs of the SVR12 rates for each treatment group will be displayed by HCV genotype (1a, 1b, and other if applicable) and total for each subgroup outlined in Section 3.4.1.

A Forest plot will graphically present the point estimates and the 2-sided 95% exact CIs of SVR12 rates for each subgroup by treatment group.

6.2. Secondary Efficacy Endpoints

6.2.1. Definition of Secondary Efficacy Endpoints

Secondary HCV efficacy endpoint includes the following:

• The percentage of subjects with HCV RNA < LLOQ (ie, < 15 IU/mL) at 4 weeks after cessation of LDV/SOF (SVR 4);

Secondary HIV efficacy endpoints include the following:

• The percentage of subjects with HIV-1 RNA ≥ 50 copies/mL 24 weeks after start of the HIV study drug as determined by the US FDA-defined snapshot algorithm {U. S. Department of Health and Human Services 2015}.

6.2.2. Analysis Methods for Secondary Efficacy Endpoints

6.2.2.1. Analysis of Secondary HCV Endpoint

SVR4 will be analyzed using exactly the same methods used for SVR12, including those used in subgroup analysis for SVR12.

6.2.2.2. Analysis of Secondary HIV Endpoints

The analysis of percentage of subjects with HIV-1 RNA \geq 50 copies/mL 24 weeks after start of the HIV study drug will be determined by US FDA-defined Snapshot algorithm.

US FDA-defined Snapshot Algorithm

The snapshot analysis window is defined as from Study Day 155 to Study Day 196, inclusive. All HIV-1 RNA data collected on-HIV-treatment (ie, data collected up to 1 day after permanent discontinuation of HIV study drug or all available data for subjects who were still on HIV study drug) will be used in the US FDA-defined snapshot algorithm. Virologic outcome will be defined as the following categories:

- HIV-1 RNA < 50 copies/mL: this includes subjects who have the last available on-HIV-treatment HIV-1 RNA < 50 copies/mL in the snapshot analysis window
- HIV-1 RNA \geq 50 copies/mL: this includes subjects
 - 1) Who have the last available on-HIV-treatment HIV-1 RNA \geq 50 copies/mL in the snapshot analysis window, or
 - 2) Who do not have on-HIV-treatment HIV-1 RNA data in the snapshot analysis window and
 - a) Who discontinue HIV study drug prior to or in the snapshot analysis window due to lack of efficacy, or
 - b) Who discontinue HIV study drug prior to or in the snapshot analysis window due to AE or death and have the last available on-HIV-treatment HIV-1 RNA ≥ 50 copies/mL, or
 - c) Who discontinue HIV study drug prior to or in the snapshot analysis window due to reasons other than AE, death, or lack of efficacy and have the last available on-treatment HIV-1 RNA ≥ 50 copies/mL.
- No Virologic Data in the Snapshot Window: this includes subjects who do not have on-treatment HIV-1 RNA data in the snapshot analysis window because of the following:
 - 1) Discontinuation of HIV study drug prior to or in the snapshot analysis window due to AE or death and the last available on-HIV-treatment HIV-1 RNA < 50 copies/mL, or
 - 2) Discontinuation of HIV study drug prior to or in the snapshot analysis window due to reasons other than AE, death, or lack of efficacy and the last available on-HIV-treatment HIV-1 RNA < 50 copies/mL or,
 - 3) Missing data during the window but on HIV study drug.

The flowchart of the US FDA-defined snapshot algorithm is provided in Appendix 2.

Summary and Inference of Virologic Outcomes

The virologic outcomes 24 weeks after start of the HIV study drug for the US FDA-defined snapshot algorithm will be listed.

Note: For treatment-experienced virologically suppressed study population, the US FDA-defined snapshot algorithm classifies subjects who discontinue study drug due to AE or death and have the last available on-HIV-treatment HIV-1 RNA value ≥ 50 copies/mL in the "HIV-1 RNA ≥ 50 copies/mL" category.

The number and percentage of subjects with HIV-1 RNA < 50 copies/mL, HIV-1 RNA ≥ 50 copies/mL, and reasons for no virologic data during the snapshot analysis window will be summarized by treatment group and overall using HIV FAS. The 95% CIs for percentage of subjects with HIV-1 RNA ≥ 50 copies/mL by treatment and overall will be constructed using the exact method.

The differences in proportion of subjects with HIV-1 RNA ≥ 50 copies/mL and HIV-1 RNA < 50 copies/mL 24 weeks after start of the HIV study drug between the 2 treatment arms and the corresponding two-sided exact 95% CIs will be calculated based on an unconditional exact methods using 2 inverted 1-sided tests. P-value from the 2-sided Fisher's exact test will also be provided.

[figure not shown]
Subgroup Analysis of Virologic Outcomes

The analysis of virologic response (HIV-1 RNA < 50 copies/mL, US FDA-defined snapshot algorithm) 24 weeks after start of the HIV study drug will be performed within each subgroup specified in Section 3.4.1 based on the HIV FAS.

6.3. Tertiary Efficacy Endpoints

6.3.1. Definition of Tertiary Efficacy Endpoints

6.3.2.1. Analysis of ALT Normalization

Tables for ALT normalization by visit will use similar methodology to the analyses of HCV RNA < LLOQ, but will use a missing – exclude analysis. Only those subjects with ALT > ULN range at baseline (defined as the last ALT value collected prior to first dose of study drug) will be included in the analysis of ALT normalization.

6.3.2.2. Analysis of HCV RNA < LLOQ while On HCV Treatment

For analyses of HCV RNA < LLOQ by visit while on HCV treatment and during the post LDV/SOF (SVR) follow-up period, subjects will be assigned a value at each visit based on the analysis window specified in Section 3.8.2.1. Missing values will be imputed based on the categorical imputation rules described in Section 3.6.1. The 2-sided 95% exact confidence interval based on the Clopper-Pearson method will be provided for the percentage of subjects with HCV RNA < LLOQ at each visit for each treatment group and overall by HCV genotype (1a and 1b). The overall category for "HCV RNA < LLOQ" will be split into the following 2 subcategories: "< LLOQ TND" for subjects with target not detected and "< LLOQ detected" for subjects with < LLOQ detected in tabular displays.

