3.6.1.2. Missing HCV RNA

For analyses of categorical HCV RNA data, missing posttreatment HCV RNA data will have the missing data imputed. Missing on-treatment HCV RNA data will be imputed up to the time of the last dose of LDV/SOF (for on-treatment displays). That is, if study days associated with the date of the last dose of LDV/SOF is greater than or equal to the lower bound of an HCV RNA analysis window, and the on-treatment value at the visit is missing, then the value will be

imputed. If the study days associated with the LDV/SOF last dose date is less than the lower bound of an HCV RNA analysis window then the on-treatment value at that visit will remain missing.

If imputation is needed following rules above, it will be proceed as below:

- If an HCV RNA data point is missing and is preceded and followed in time by values that are less than the lower limit of quantitation (LLOQ) target not detected (TND) (ie, "< LLOQ TND"), then the missing data point will be set to "< LLOQ TND".
- If an HCV RNA data point is missing and preceded and followed by values that are "< LLOQ detected", or preceded by "< LLOQ detected" and followed by "< LLOQ TND", or preceded by "< LLOQ TND" and followed by "< LLOQ detected", then the missing value will be set to "< LLOQ detected".
- In above situations the data point will be termed a bracketed success; otherwise, the data point will be termed a bracketed failure (ie, ≥ LLOQ detected).
- If a data point is missing and is not bracketed, the missing data point will also be termed a failure (ie, ≥ LLOQ detected).

For analyses of continuous HCV RNA data, when and only when a missing HCV RNA value is imputed as < LLOQ TND or < LLOQ detected according to the imputation rule described above, the corresponding continuous value will be imputed to LLOQ - 1 IU/mL. No other imputation will be performed for continuous HCV RNA data.

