3.8. Analysis Visit Windows

3.8.1. Definition of Study Day

Study Day 1, or the **first dose date of the randomized HIV study drug,** is defined as the day when the first dose of the randomized F/TAF-based regimen (ie, E/C/F/TAF or F/R/TAF) is taken, as recorded on the Study Drug Administration eCRF form.

Study Days will be calculated from Study Day 1 and derived as follows:

- For days on or after the Study Day 1 date: Assessment Date Study Day 1 date + 1
- For days prior to the Study Day 1: Assessment date Study Day 1 date.

Part 2 Day 1, or the first dose date of LDV/SOF, is defined as the day when the first dose of HCV study drug (ie, LDV/SOF) is taken, as recorded on the Study Drug Administration eCRF form.

Part 2 Days are calculated from Part 2 Day 1 and derived as follows:

- For days on or after the Part 2 Day 1 date: Assessment Date Part 2 Day 1 date + 1
- For days prior to the Part 2 Day 1: Assessment date Part 2 Day 1 date.

Last Dose Date of HIV Study Drug is the latest of the study drug end dates of E/C/F/TAF or F/R/TAF, recorded on the Study Drug Administration eCRF form with "Permanently Withdrawn" box checked for subjects who prematurely discontinued or completed the randomized HIV study drug according to the Study Drug Completion eCRF.

Last Dose Date of LDV/SOF is the latest of the LDV/SOF end dates recorded on the Study Drug Administration eCRF form with "Permanently Withdrawn" box checked for subjects who prematurely discontinued or completed LDV/SOF according to the Study Drug Completion eCRF.

If last dose date is missing (eg, only year of last dose date is known or completely missing due to lost to follow-up) for subjects who prematurely discontinued or completed study drug (E/C/F/TAF, F/R/TAF, LDV/SOF) by the data finalization date, the latest of the study drug start dates and end dates for that drug, the clinical visit dates and the laboratory visit dates (post HCV treatment visits and unscheduled visits will not be included for LDV/SOF, 30-day follow-up visit will not be included for any study drug), will be used to impute the last dose date. For other partial missing last dose date, please see the programming specifications for imputation rule details.

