3.8.2. Analysis Visit Windows

Subject visits might not occur on protocol-specified days. Therefore, for the purpose of analysis, observations will be assigned to study analysis windows, starting from Study Day 1.

In addition, for Part 2 safety analyses and LDV/SOF efficacy analyses, Part 2 analysis window will be assigned to observations except HIV-1 RNA, CD4 cell count, and CD4%, starting from Part 2 Day 1.

No analysis window will be defined for ECG data, given 12-Lead ECG is only planned for Screening and ESDD visits.

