3.8.2.1. Study Analysis Windows

The study analysis windows for HIV-1 RNA, CD4+ cell count, CD4 % are provided in Table 3-1. Note that, in convenience of HIV efficacy analyses, the visit ID of study analysis windows are named as Weeks 24 and 32 instead of post HCV Treatment Weeks 4 and 12, and these study analysis windows are assigned relative to Study Day 1.

Table 3-1. Study Analysis Windows for HIV-1 RNA, CD4+ Cell Count, and CD4 %

Visit ID	Nominal Day	HIV-1 RNA	CD4+ Cell Count and CD4 %
Baseline		≤1	≤1
Week 4	28	[2, 35]	[2, 42]
Week 6 ^a	42	[36, 49]	N/A ^b
Week 8	56	[50, 70]	[43, 70]
Week 12	84	[71, 98]	[71, 98]
Week 16	112	[99, 126]	[99, 126]
Week 20	140	[127, 154]	[127, 154]
Week 24	168	[155, 196]	[155, 196]
Week 32	224	≥ 197	≥ 197

a Only HIV-1 RNA is planned for Week 6 assessment;

The analysis windows for weight, vital signs, metabolic assessments, laboratory tests, and bone and renal biomarkers collected up to the last dose date of LDV/SOF + 3 days are provided in Table 3-2.

Table 3-2. Study Analysis Windows for HCV RNA^a, Weight, Vital Signs^b, Metabolic Assessments, and Laboratory Tests^c

Visit ID	Nominal Day	HCV RNA ^d	Laboratory Tests, Weight, and Vital Signs	Fasting Glucose and Lipid Panel ^d	Bone and Renal Biomarkers ^e
Baseline		≤ 1	≤1	≤ 1	≤ 1
Week 4	28	N/A	[2, 42]	N/A	[2, 42]
Week 8	56	≥ 2	[43, 70]	[2, 98]	[43, 70]
Week 12	84		[71, 98]	N/A	[71, 112]
Week 16	112	N/A	[99, 126]		N/A
Week 20	140		≥ 127	≥ 99	≥ 113

a For HCV RNA, this analysis window will be applied to data collected up to the first dose date of LDV/SOF only. Therefore, no Weeks 12-20 study analysis window is assigned to HCV RNA;

b N/A = not applicable;

b Vital signs include resting blood pressure, pulse, respiratory rate and temperature;

- c Laboratory tests include chemistry, hematology, and coagulation profiles, estimated GFR, urinalysis and urine chemistry (except urine albumin), and urine pregnancy test. Note that visit schedule of urine protein to creatinine ratio (UPCR) is same as that of urine chemistry;
- d Lipid panel includes total cholesterol, HDL, direct LDL, triglycerides.
- e Bone and renal biomarkers include parathyroid (PTH) and serum OH-25 vitamin D; retinol binding protein, beta-2-microglobulin, and urine albumin. Note that visit schedule of urine albumin to creatinine ratio (UACR) is the same as that of urine albumin.

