3.8.2.2. Part 2 Analysis Windows for HCV RNA and Part 2 Safety Data

For clearity of by-visit summary, the visit IDs of Part 2 analysis windows corresponding to the protocol planned visits Week 8, Week 12, Week 16, and Week 20 are renamed to Part 2 Baseline, Week 4, Week 8, and Week 12 respectively, as counted starting from Part 2 Day 1. Data of HCV RNA and safety assessments collected up to the last dose date of LDV/SOF + 3 days are considered to be **on-LDV/SOF data**. The Part 2 analysis windows for on-LDV/SOF HCV RNA, weight, vital signs, metabolic assessments, laboratory tests, and bone and renal biomarkers are provided in Table 3-4.

Table 3-4. Part 2 Analysis Windows^a for On LDV/SOF Data from HCV RNA, Weight, Vital Signs, Metabolic Assessments, and Laboratory Tests

Visit ID	Nominal LDV/SOF Day ^b	HCV RNA, Laboratory Tests, Weight, and Vital Signs	Fasting Glucose and Lipid Panel	Bone and Renal Biomarkers
Part 2 Baseline		≤1	≤ 1	≤ 1
Week 4	28	[2, 42]	N/A	[2, 56]
Week 8	56	[43, 70]	IN/A	N/A
Week 12	84	≥71	≥ 2	≥ 57

- a This analysis window will be applied to data collected up to the last dose date of LDV/SOF + 3 days;
- b This analysis window will be calculated from Part 2 Days defined in Section 3.8.1.

The Part 2 analysis windows for post LDV/SOF data from HCV RNA, weight, vital signs, metabolic assessments, laboratory tests, and bone and renal biomarkers is the same as the study analysis windows specified in Table 3-3.

3.8.3. Selection of Data in the Event of Multiple Records in an Analysis Visit Window

Depending on the statistical analysis method, single values may be required for each analysis window. For example, change from baseline by visit usually requires a single value, whereas a time-to-event analysis would not require one value per analysis window. When a single value is needed, the following rule(s) will be used:

If multiple nonmissing numeric observations exist in a window, records will be chosen as follows:

- For both Study and Part 2 baselines, the last available record on or prior to the dates of the first dose dates of HIV and HCV study drugs, respectively, will be selected. If there are multiple records with the same time or no time recorded on the same day, average (arithmetic mean) will be used for the baseline value, except for HIV-1 RNA (see below).
- For postbaseline visits:
 - For CD4+ cell count, CD4%, and post LDV/SOF HCV RNA, the record(s) collected on the lastest day in the window will be selected for anlaysis.

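### On-treatment HCV RNA: SAP 6.3.2.2 cites a section with no on-LDV/SOF window, and the imputation rule in 3.6.1.2 names the wrong day count (minor)

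*SAP*

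**What the plan says.** SAP 6.3.2.2 covers the proportion with HCV RNA < LLOQ by visit, both on HCV treatment and in follow-up. For both it states that "subjects will be assigned a value at each visit based on the analysis window specified in Section 3.8.2.1".

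Section 3.8.2.1 holds two tables with an HCV RNA column. In Table 3-2 the column has only Baseline and Week 8, and footnote a says "this analysis window will be applied to data collected up to the first dose date of LDV/SOF only". The footnote continues: "Therefore, no Weeks 12-20 study analysis window is assigned to HCV RNA". Table 3-3 gives the follow-up windows, FU-4 [21, 69] and FU-12 [70, 146], counted from the last LDV/SOF dose.

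Section 3.8.2 sets the general rule: "for Part 2 safety analyses and LDV/SOF efficacy analyses, Part 2 analysis window will be assigned to observations", with HIV-1 RNA and CD4 excepted. The on-LDV/SOF windows follow in Section 3.8.2.2, Table 3-4: Week 4 [2, 42], Week 8 [43, 70] and Week 12 from 71 onward. Its footnote b fixes the clock: "This analysis window will be calculated from Part 2 Days defined in Section 3.8.1".

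Section 3.6.1.2 decides when a missing on-treatment value is imputed. The condition is "if study days associated with the date of the last dose of LDV/SOF is greater than or equal to the lower bound", the bound being that for the visit in question. If the last dose falls before that bound, the value is to stay missing. Section 3.8.1 defines two clocks: "Study Days will be calculated from Study Day 1 and derived as follows", with Study Day 1 being the first dose of the randomized HIV drug, and Part 2 Days, counted from the first LDV/SOF dose.

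**The concern.** There are two separate slips, and each concerns which clock applies to HCV RNA while LDV/SOF is being taken.

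First, the reference in 6.3.2.2 sends on-treatment visits to a section that expressly has no window for them.

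Second, once the reader has moved to Table 3-4, the rule in 3.6.1.2 sets a day count that the SAP defines from the HIV switch against bounds counted from the LDV/SOF start. The two clocks are about eight weeks apart, so the test is met far too early. A subject who stopped LDV/SOF early would then receive imputed on-treatment results for visits after stopping. The imputed result is a failure, or a success if values < LLOQ lie on both sides. That is what the rule was written to prevent.

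**Working it through.** **Inputs**
- Nominal Study Days for Weeks 8, 12, 16 and 20 are 56, 84, 112 and 140 (SAP Tables 3-1 and 3-2).
- Table 3-4 has nominal days 28, 56 and 84, with lower bounds 2, 43 and 71, in Part 2 Days.
- LDV/SOF starts at Week 8 (Protocol 6.4.1). If the Week 6 HIV-1 RNA must be repeated, the start may be 2 to 4 weeks later (Protocol 6.9.1), so about Study Day 70 to 84.

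**Step 1: reproduce the plan's figures.** Shifting the protocol visits by the nominal LDV/SOF start gives 84 − 56 = 28, 112 − 56 = 56 and 140 − 56 = 84. These are the Table 3-4 nominal days, so Table 3-4 is the protocol schedule moved to the LDV/SOF clock.

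**Step 2: the reference.** Of the three on-treatment HCV RNA visits (LDV/SOF Weeks 4, 8 and 12), Section 3.8.2.1 supplies a window for none and Section 3.8.2.2 for all three. Both follow-up visits have a window in Section 3.8.2.1, in Table 3-3.

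**Step 3: the imputation test.** Let S be the Study Day of the first LDV/SOF dose and L the Part 2 Day of the last. The last dose then falls on Study Day S + L − 1.
- Part 2 Day reading: impute a missing Week 8 value if L ≥ 43, and a missing Week 12 value if L ≥ 71.
- Literal reading: impute Week 8 if S + L − 1 ≥ 43, that is L ≥ 44 − S. Impute Week 12 if S + L − 1 ≥ 71, that is L ≥ 72 − S.

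The table shows the last-dose days on which the literal rule imputes although the Part 2 Day rule would not.

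| S | Week 8 | Week 12 |
|---|---|---|
| 54 | Days 1-42 | Days 18-70 |
| 56 (nominal) | Days 1-42 | Days 16-70 |
| 58 | Days 1-42 | Days 14-70 |
| 70 (2-week delay) | Days 1-42 | Days 2-70 |
| 84 (4-week delay) | Days 1-42 | Days 1-70 |

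Week 4 differs only for a subject whose last dose is on Day 1.

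**Example.** LDV/SOF starts on Study Day 56 and the last dose is on Part 2 Day 28. The last dose is Study Day 56 + 28 − 1 = 83. On Part 2 Days, 28 is below both 43 and 71, so Weeks 8 and 12 stay missing. On Study Days, 83 exceeds both bounds, so both are imputed.

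**Step 4: effect per subject.** Assume the planned 60 per arm, all others < LLOQ, and values left missing dropped from the denominator. One wrongly imputed failure turns 59/59 (100%) into 59/60 (98.3%), a change of 1.7 points. A bracketed success turns 59/59 into 60/60, which is no change.

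**The case against.** The strongest reply is that the SAP already shows what it means. Section 3.8.2 assigns Part 2 windows to LDV/SOF efficacy, Section 3.8.2.2 is titled for HCV RNA, and the Table 3-2 footnote tells the programmer that the study windows do not reach this period. Someone following 6.3.2.2 would find no window and turn to Table 3-4. This stands, and it is why the reference is an error of citation and not of method. A reader might infer that the by-visit table would contain no observed on-treatment data; the rest of the SAP does not support that.

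A reader might also add the two slips together. They do not add: the second arises only once Table 3-4 is in use, which means the first has been resolved.

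On the second slip, *study days* in 3.6.1.2 is in lower case, and the stated purpose of the rule points to the LDV/SOF clock. That is a fair reading of intent. But the term's only definition in the SAP runs from the first HIV dose, and Part 2 Days was available as a separate term. Unlike the missing window, this slip would not show itself when programmed.

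Finally, few subjects will stop early. Protocol Table 1-1 gives discontinuation rates of 0 to 1% for 12 weeks of LDV/SOF, and 0 in the coinfected study. At those rates, 0 to about 1 of 120 would be affected (0.01 × 120 = 1.2). The table does not say whether it counts all causes, so this is only a guide. In addition, on-LDV/SOF data run to 3 days after the last dose. A stop just below a bound (Days 40-42 or 68-70) may therefore have an observed value in the window and nothing to impute.

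**Conclusion.** Both sentences are wrong as written, and the severity is minor. The reference in 6.3.2.2 fails for the three on-treatment visits and is right for follow-up. The test in 3.6.1.2, taken literally from a Study Day 56 start, imputes missing values that should stay missing: at Week 8 for a last dose on Part 2 Day 1-42, and at Week 12 for one on Day 16-70. The Week 12 range widens if LDV/SOF starts late.

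The reach is narrow: the by-visit on-treatment display among the tertiary endpoints, and bracketed values in the log10 HCV RNA summary of 6.3.2.3, which borrows the same imputation. Only subjects who stop LDV/SOF early are exposed.

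A reader might infer that SVR4 or SVR12 is at risk. Neither is. Their windows are in Table 3-3 and count from the last LDV/SOF dose, and missing post-treatment values are imputed without the day comparison.

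The day ranges rest on the nominal Week 8 start and on giving *study days* its defined meaning. The 1.7-point figure rests on the assumptions in Step 4, including 60 per arm, which is the planned number randomized; the HCV FAS may be smaller.

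**What to change.** Make two wording edits in the SAP.

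1. In 6.3.2.2, cite Section 3.8.2.2 (Table 3-4) for on-LDV/SOF visits and Table 3-3 for post-LDV/SOF visits. Naming the tables also separates the two visits labelled Week 8: the Table 3-2 one, up to the first LDV/SOF dose, and the Table 3-4 one, on treatment.
2. In 3.6.1.2, replace *study days* with *Part 2 Days* in both sentences of the on-treatment rule, and name Table 3-4 as the source of the lower bound.

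No new data, analyses or changes in sample size are needed.
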